TMS in Primary Progressive Aphasia: Modulation of Brain Networks and Language

NCT Number: NCT04188067

Date: September 9th, 2025

SYNOPSIS

Project title: TMS in Primary Progressive Aphasia: Modulation of Brain Networks and Language

Objective: The objective of this study is to assess the potential transient and durable benefits of repetitive transcranial magnetic stimulation (rTMS) to behavior and brain network in the three variants of Primary Progressive Aphasia (PPA): logopenic, semantic and nonfluent PPA.

Study Period:

Planned enrollment duration: 30 months

Planned study duration: 3 months per participant

Number of Patients: 10

Study Intervention:

Repetitive transcranial magnetic stimulation (rTMS) has emerged as a potential treatment option for Primary Progressive Aphasia. rTMS can induce long-term plastic changes and selectively alter functional network connectivity, which may improve symptoms related to language and cognition. In this study, resting state functional MRI (rsfMRI) is used before rTMS to localize an individually optimized target for stimulation, and after rTMS to measure effects of stimulation on network functional connectivity and language.

Experimental Design:

This study follows a double-blinded, placebo-controlled, cross-over experimental protocol. Participants are randomized to start with either active or sham rTMS during 10 weekdays (Monday through Friday), over 2 consecutive weeks. Intervention arms are separated by a four-week washout period. Language assessments, MRI assessments, and questionnaires are included at the baseline timepoint and after the end of both active and sham arms. A follow-up timepoint including a language assessment is conducted three weeks after the end of Arm 2.

Inclusion criteria:

1. Between the ages of 40-99
2. All participants are native English speakers

3. Willing and able to consent to the protocol and undergo imaging and neuropsychological testing at the specified time points
4. Patients with very mild or mild PPA are included.

Exclusion criteria:

1. History of head trauma involving loss of consciousness or alteration in consciousness
2. Another major neurologic or psychiatric condition
3. Known presence of a structural brain lesion (e.g. tumor, cortical infarct)
4. Any contraindication to MRI, such as presence of pacemakers, aneurysm clips, artificial heart valves, ear implants, metal fragments, or foreign objects in the eyes, skin, or body

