The target for rTMS is in the left dorsolateral prefrontal cortex. Accuracy and reproducibility of targeting is achieved with a frameless stereotactic optical tracking neuronavigation system (e.g. Brainsight™ or Localite), which permits real-time monitoring of coil placement and head position. Sham stimulation is delivered to the exact same cortical targets. While no electromagnetic stimulation is delivered during sham, the sounds will approximate active stimulation, and skin electrodes will approximate the sensation of active rTMS.

For all sessions, rTMS is delivered at 80-120% of a patient's resting motor threshold. The resting motor threshold is determined by the minimal stimulus intensity to elicit movement of the contralateral first dorsal interosseous muscle-or to elicit a motor evoked potential (MEP) of at least 50 μ V-on three out of six trials. rTMS is administered in an excitatory pattern as intermittent burst stimulation (iTBS) (bursts of 3 pulses of 50Hz rTMS). Parameters are well within established safety guidelines (Rossi et al. 2009).

Primary outcomes:

Language Performance: The primary outcome is the change in language performance as measured by Boston Naming Test (BNT) before and after TMS.

Brain network connectivity: The main neural outcome measure is the relative change in z-transformed correlation coefficients between regions of the language brain network before and after TMS.

Statistical Analysis:

Language performance: A within-subjects repeated measures ANOVA is used to compare the change in language performance following active rTMS condition versus the sham stimulation condition.

Brain network connectivity: A within-subjects repeated measures ANOVA is used to compare the change in language brain network functional connectivity following active rTMS condition versus the sham stimulation condition.

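### The cross-over ANOVA for both primary outcomes has no stated period term, and balance of the two treatment orders is not stated

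*Combined protocol and SAP*

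**What the plan says.** The Experimental Design section of the Synopsis describes the trial so: "This study follows a double-blinded, placebo-controlled, cross-over experimental protocol". Order is random ("Participants are randomized to start with either active or sham rTMS"), but no ratio, blocking or other balancing rule is given. The sample size is stated as "Number of Patients: 10".

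On timing, "Intervention arms are separated by a four-week washout period", and each arm lasts two weeks. On visits, "Language assessments, MRI assessments, and questionnaires are included at the baseline timepoint and after the end of both active and sham arms". One baseline is listed, and no separate assessment before Arm 2.

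The Statistical Analysis section gives one sentence per primary outcome. For language: "A within-subjects repeated measures ANOVA is used to compare the change in language performance following active rTMS condition versus the sham stimulation condition". For connectivity, the same ANOVA is "used to compare the change in language brain network functional connectivity following active rTMS condition versus the sham stimulation condition". Neither sentence names period, order or sequence. Neither excludes such a term, but nothing else in the document supplies one.

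**The concern.** In a cross-over, each participant's active-minus-sham difference contains the treatment effect and whatever changed between the two periods. Here two sources of change are plausible. Disease progression could affect both outcomes, and repeating the Boston Naming Test could affect the language outcome. They may partly offset each other.

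A change score does not protect against this if both changes are taken from the single listed baseline, because that baseline cancels when sham is subtracted from active. What remains is post-active minus post-sham, measured about 4 + 2 = 6 weeks apart.

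An ANOVA with condition as its only factor, at two levels, is a paired t-test. It treats a shift in one of two ways:

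- **Equal orders:** the shift cancels from the mean but inflates the error term, so the interval widens and power falls.
- **Unequal orders:** part of the shift also enters the estimate. A 10-patient trial reports only the split it obtained.

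**Working it through.** **Inputs from the documents:** n = 10, two periods, random order, post-arm visits about 6 weeks apart. The plan gives no power, effect size, SD or alpha, so it has no figure to reproduce.

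**Assumptions:** two-sided 0.05, no dropout, true effect τ of 0 or 1, and a shift π (period 2 minus period 1) of 0.25, 0.5 or 1.0. Both τ and π are in units of the SD of the within-person difference.

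**Model:** d = τ − π + error for active-first and d = τ + π + error for sham-first, with error SD 1. As a check with change from one shared baseline, a decline of 0.5 SD between arms (π = −0.5) at τ = 1 gives mean differences of 1.50 SD (active first) and 0.50 SD (sham first). The shared baseline does not remove the shift.

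**Without the term** (paired t, 9 df):

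- Bias given the split = π × (n sham-first − n active-first)/10. Its size is 0.2π at 6/4, 0.4π at 7/3 and 0.6π at 8/2. For π = 0.5 that is 0.10, 0.20 and 0.30 SD.
- At 5/5 the bias is 0 and the expected residual variance is 1 + (10/9)π². The error term is inflated by √(1 + (10/9)π²) = 1.03, 1.13 and 1.45.

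**With the term** (mean of the two sequence means, 8 df): SE = 0.5 × √(1/n₁ + 1/n₂). The estimate is unbiased at every split and does not depend on π.

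**Results at 5/5** (power at τ = 1; simulation with 200,000 replicates per scenario, agreeing with numerical integration):

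| Shift (SD) | Power without | Power with | Type I error without | Mean interval width, without ÷ with |
|---|---|---|---|---|
| 0.25 | 78% | 79% | 4.4% | 1.4395/1.4138 = 1.02 |
| 0.5 | 72% | 79% | 3.0% | 1.5752/1.4148 = 1.11 |
| 1.0 | 48% | 79% | 0.7% | 2.0365/1.4139 = 1.44 |

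The two analyses have equal power at 5/5 when the shift is about 0.2 SD.

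**Type I error without the term at unequal splits** (5% throughout with it):

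| Split | 0.25 SD | 0.5 SD | 1.0 SD |
|---|---|---|---|
| 6/4 | 4.6% | 3.7% | 1.7% |
| 7/3 | about 5% | about 6% | about 6% |
| 8/2 | 6.6% | 10.6% | 20% |

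The direction of imbalance matters too. At 7/3 with a 0.5 SD shift and τ = 1, unadjusted power is 88% or 53%, depending on which order is over-represented. With the term it is 72% either way.

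**How likely each split is**, if randomisation is simple (an assumption): 5/5 has probability 252/1024 = 25%, 6/4 has 420/1024 = 41%, 7/3 has 240/1024 = 23%, and 8/2 or worse has 112/1024 = 11%. Averaged over these:

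- Unadjusted type I error is 5.0%, 5.0% and 5.2% at the three shifts.
- Unadjusted power is 78%, 71% and 50%, against 74% adjusted. The adjusted average leaves out 10/0 (probability 0.2%), where the term cannot be fitted.
- Without balanced order, therefore, the term gains power on average only above a shift of about 0.4 SD.

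**The case against.** The strongest reply is that this is missing detail in a synopsis-style document, and that the harm depends on a quantity nobody has supplied. The named method is compatible with an order factor and with blocked randomisation. Nothing in the documents shows a shift of 0.5 SD over about 6 weeks in very mild or mild disease, and for connectivity test practice is not a source. If each arm did have its own pre-arm measurement, a steady drift would largely cancel. Over repeated randomisations the unadjusted estimate is unbiased and type I error is about 5%. Clear inflation appears only at splits of 8/2 or worse. The term can also cost power when orders are unequal and the shift is small.

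Most of this stands, and it limits the weight of the point. It does not remove it. The document is the combined protocol and SAP and contains no other analysis text. It lists one baseline, so a shared baseline is the natural reading. Correct behaviour on average does not help the reader of one 10-patient result whose estimate moves with the split obtained. Leaving the term open also allows the choice to be made after the data are seen, when the two analyses could differ materially. The power cost at unequal splits is a reason to balance the order as well as to specify the term.

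**Conclusion.** The point holds and should be fixed. Neither primary analysis specifies a period or sequence term, and balance of order is not stated. The consequence is conditional on a net shift between periods. It is negligible at 5/5 up to about 0.2 SD, a loss of about 7 percentage points of power at 0.5 SD (79% to 72%), and about 31 points at 1.0 SD (79% to 48%). At an unequal split there is also a bias of 0.2 to 0.6 times the shift for splits from 6/4 to 8/2. Overall type I error is not threatened.

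These sizes rest on the assumed alpha, effect and range of shifts, and on both changes being taken from one baseline. Confidence is medium because the documents do not give the size of the shift.

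**What to change.** Before unblinding, make these changes for both primary outcomes:

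- Specify a cross-over model with treatment and period as fixed effects and participant as the repeated unit. Equivalently, add sequence as a between-subjects factor with its interaction with condition, and average the condition effect equally over the two sequences. A main effect of sequence alone would not remove the shift.
- State which baseline each change score uses.
- State how order is allocated. Where allocation is still open, block it towards 5/5, with the blocking concealed from those who enrol, because the last allocations in a small block can become predictable.
- Report the split obtained.

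The cost is SAP wording, plus blocking of any remaining allocations. At 5/5 one degree of freedom is lost (9 to 8). The effect detectable with 80% power rises from 0.996 to 1.012 SD, and power at 1 SD falls from 80% to 79% if there is no shift. At unequal splits the term costs more: the detectable effect is 1.033 SD at 6/4, 1.104 SD at 7/3 and 1.265 SD at 8/2, with power at 1 SD of 77%, 72% and 60%. That is why the term and balanced order belong together. The period term does not address carryover, which needs separate treatment.

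### The repeated measures ANOVA named for both primary outcomes drops anyone lacking a post-arm value; a mixed model including baseline would recover part of that loss, at a small, nameable cost

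*Combined protocol and SAP*

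**What the plan says.** The Synopsis gives "Number of Patients: 10". Under Experimental Design, "This study follows a double-blinded, placebo-controlled, cross-over experimental protocol", and "Participants are randomized to start with either active or sham rTMS during 10 weekdays". On timing, "Language assessments, MRI assessments, and questionnaires are included at the baseline timepoint and after the end of both active and sham arms", and "Intervention arms are separated by a four-week washout period". A later visit is also planned: "A follow-up timepoint including a language assessment is conducted three weeks after the end of Arm 2". The analysis does not mention it.

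Statistical Analysis consists of one sentence per primary outcome. For language: "A within-subjects repeated measures ANOVA is used to compare the change in language performance following active rTMS condition versus the sham stimulation condition". For connectivity: "A within-subjects repeated measures ANOVA is used to compare the change in language brain network functional connectivity", again active against sham.

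The documents state no missing-data rule, analysis set, dropout allowance, replacement rule or sensitivity analysis. They do not say in words that incomplete participants are excluded. That follows from the standard form of the named method.

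**The concern.** A two-condition within-subjects ANOVA works on each person's active-minus-sham difference. The documents describe one baseline shared by both arms, so it cancels: (post-active − baseline) − (post-sham − baseline) = post-active − post-sham. Without one of the two post-arm values there is no difference to analyse, and the observed baseline and other post-arm value go unused.

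Two things are at stake. The first is precision, because 10 participants leave little to spare. The second is a possible bias. If people who do poorly in arm 1 leave, and active stimulation works, more of them will come from the sham-first sequence. The remaining sham results then look too good and the contrast shrinks. The same applies to connectivity, where each assessment also needs a usable scan.

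**Working it through.** The plan gives no alpha, power, effect size, SD, correlation or dropout rate, so there is no sponsor figure to reproduce.

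**Inputs from the documents:** N = 10; two periods; assessments at baseline and after each arm; arm 2 ends at about week 2 + 4 + 2 = 8.

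**Assumptions:** 5 participants per sequence; two-sided 0.05; equal between-visit correlation ρ from 0.5 to 0.9; dropout rates as labelled.

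**1. Chance of any loss.** If each participant is incomplete with probability d, P(at least one of 10) = 1 − (1 − d)^10. This is 40% at d = 5%, 65% at 10% and 89% at 20%. For at least two lost, the figures are 9%, 26% and 62%.

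**2. Paired power at a standardised difference of 1.0** (noncentral t, n − 1 degrees of freedom, noncentrality √n):

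| Complete participants | Power | Difference detectable with 80% power |
|---|---|---|
| 10 | 80% | 1.00 |
| 9 | 75% | 1.07 |
| 8 | 68% | 1.16 |
| 7 | 60% | 1.27 |

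**3. Variance of the contrast, losses after arm 1.** Suppose n per sequence are complete and m per sequence have only baseline and arm 1. In units of the outcome variance, completers contribute information n/(1 − ρ). Incomplete participants contribute m/[2(1 − ρ²)]. The full design has 5/(1 − ρ). The variance ratios to full data are:

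- complete cases: 5/n
- mixed model with baseline: 5/[n + m/(2(1 + ρ))]

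For two lost, one per sequence (n = 4, m = 1):

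- complete cases: 5/4 = 1.25
- mixed model, ρ = 0.5: 5/(4 + 1/3) = 1.154
- mixed model, ρ = 0.9: 5/(4 + 1/3.8) = 1.173

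For three lost (4 and 3 complete), the period-adjusted complete-case ratio is (1/4 + 1/3)/(1/5 + 1/5) = 1.458. Generalised least squares on all observed data gives 1.265-1.301. The ANOVA without a period term gives 10/7 = 1.43.

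**4. Limits of the gain.**

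- For participants lost before the first post-arm assessment, the mixed model gives 1.25 with two lost, the same as complete cases.
- Without baseline in the model, the ratio is 5/[n + m(1 − ρ)/2]. At ρ = 0.9 this is 5/4.05 = 1.235, so only about 6% of the lost variance is recovered: (1.25 − 1.235)/0.25.

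**5. Power of the two analyses.** In simulation (N = 10, two lost after arm 1, equal correlation, true difference 1 SD), power was about 0.68 for the ANOVA and 0.77 for the mixed model. Type I error was near 5% for both. Part of the gain comes from pooling residual error over three visits: with complete data, 30 − 10 − 2 − 1 = 17 residual degrees of freedom against 9.

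**6. Bias.** This was simulated with N = 10, ρ = 0.8 and about 2,500-3,000 trials per scenario, in SDs of the paired difference:

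| Dropout assumption | ANOVA | Mixed model |
|---|---|---|
| Random | about 0 | about 0 |
| Poor first-arm response, no true effect | at most 0.02 | at most 0.02 |
| Poor first-arm response, true effect 1 SD | −0.05 | −0.01 |
| Poor responders in sham-first sequence only | about −0.10 | −0.01 to −0.02 |

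**7. What the mixed model assumes.** A single random participant effect imposes equal correlation between visits. Suppose instead that correlation is r per two weeks and the visits fall at weeks 0, 2 and 8. The true variance of a paired difference is 2(1 − r³), but the model pools to about 2[1 − (r + r³ + r⁴)/3]. At r = 0.80 the ratio is 0.852/0.976 = 0.87; at r = 0.95 it is 0.252/0.285 = 0.88. The contrast variance is therefore understated by about 12-13%. With complete data and no effect, simulated type I error was 6.3-6.6% for the mixed model and 4.9-5.1% for the ANOVA.

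**The case against.** The planned paired analysis is valid with complete data and needs no assumption about correlation between visits, whereas its replacement does (step 7). That stands. A reader might infer that the mixed model is a free improvement, and it is not. It also needs small-sample degrees of freedom: a large-sample z test rejected 5.9-6.9% of the time under no effect, against 4.5-5.0% with t degrees of freedom. It relies on data missing at random, so dropout driven by unobserved results remains a problem.

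A reader might also infer that the ANOVA is seriously biased. The calculations do not support this. Dropout related to baseline or to a person's overall level cancels in the within-person difference. With no treatment effect the ANOVA's type I error stayed at 4.2-5.3%. The bias of about 0.05 SD is small beside a standard error of 1/√10 = 0.32 SD, and it works against finding a benefit.

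A third inference, that substantial dropout is to be expected, has no basis in the documents. They give no rate, and they partly guard against loss: inclusion is limited to very mild or mild disease, and exclusion items 6 and 7 cover compliance and willingness to return. The three-week follow-up lies outside the contrast, so the exposed period is about 8 weeks.

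What does not stand is that the choice of model is mere preference. The data a mixed model would use are already scheduled for collection, and the plan does not say how an incomplete participant would be handled.

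**Conclusion.** The concern holds as a conditional one. In its standard form the named method uses only participants with both post-arm values, and at N = 10 each loss after arm 1 costs about 10% of the sample. If two are lost at that stage, variance rises 25% under the ANOVA and 15-17% under a mixed model with baseline, so roughly 31-38% of the lost variance is recovered. This assumes equal correlation of 0.5-0.9 and one loss per sequence. Recovery is nil for losses before the first post-arm assessment. The bias in completers is small and towards no effect under the dropout patterns examined. The actual size cannot be fixed from the documents, because they give neither a dropout rate nor a correlation.

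**What to change.** Before unblinding, specify for both primary outcomes a linear mixed model fitted by REML to all baseline and post-arm values of every randomised participant. Use fixed effects for condition and visit (period), a random participant effect and Kenward-Roger degrees of freedom, with active minus sham as the primary estimate. State the missing-at-random and equal-correlation assumptions. Report the complete-case paired ANOVA as a sensitivity check; it also protects against a wrong correlation structure.

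This costs a few lines of analysis text and uses standard software, with no new visits, data or participants. The statistical price is one degree of freedom for period and the mild type I error inflation in step 7 if correlation decays over time. With complete data and balanced sequences the point estimate matches the ANOVA's.
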